Figure 1: Illustration of Bronfenbrenner's ecological framework by Mash in 2019

The PPPM guides us through the planning process to avoid missing aspects important to a project by first knowing the outcomes, and then walking back to address some factors that will enable us to reach our expected results.

Predisposing,

Reinforcing and

Enabling Constructs in

Educational

Diagnosis and

Evaluation; aim to map educational 'diagnoses and planning' [48].

Policy,

[figure not shown]
Regulatory, and

Organisational Constructs in

Educational/Ecological and

Environmental

Development (guides socio-ecological assessment and planning) [48,49].

We will be using these two as the components of the former are incorporated in the later.

Predisposing Factors to performing skills from the YoFA program taught:

Knowledge (Training given), attitudes, and practices, motivation, self-efficacy.

Enabling factors: Antecedents of behaviour that facilitate motivation to perform the behaviour e.g., accessibility to FA “Stop the bleed” kit, to a telephones availability of a teacher to guide them through, and Health facility to receive the patient, skills, and laws.

Reinforcing factors: Rewards or punishments following or anticipated as a consequence of behaviour e.g., does the family encourage the child to learn the FA skills and apply what is learnt? What is/are the thoughts of peers, teachers, and other stakeholders? (here we see the interpersonal and community aspects of the ecological model come into place).

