3.5 SAMPLE SIZE AND SAMPLING

Sample Size Calculation

For the cross-sectional study and Intervention

Assuming an equal number of control and intervention subjects, a prevalence of the outcome in the controls of 0.5, and a prevalence in the intervention group of 0.75 (an absolute increase of 25%)[17] with a power of 80% and 5% error margin, we calculated the sample size needed using STATA.

Estimated sample sizes for a two-sample proportions test Pearson's chi-squared test using STATA

$H_0: p_2 = p_1$ versus $H_a: p_2 \neq p_1$ Study parameters:

```
alpha = 0.0500
power = 0.8000
delta = 0.2500 (difference)
p1 = 0.5000
p2 = 0.7500
```

Estimated sample sizes:

N =	116
N per group =	58

If we assume a 15% drop out rate, we have a sample size of $15\% * 116 = 17.4$ Thus, sample size is $116 + 17.4 = 133.4 \approx 134$

For each group, the sample needed is therefore **N = 67 students. Sampling**

Since this is a crisis area, we will use convenience sampling to choose the Health Areas (HAs) that are secure and geographically accessible (safest) in both HDs. Out of seven (7) and eight (8) HAs in Buea and Tiko HDs respectively, there are 4 accessible HAs in each. Of these, one HA from each HD does not harbour a state secondary school (SSS).

Leaving us with 3 HAs to work with in each HD. Each of these HAs contains 1 SSS but for 1 HA from each District which has 2 SSSs. We would work with all these State schools to ensure that we get students from most of the communities around the schools, thus ensuring the representativeness of our samples. To avoid spill-over, one of the districts will be selected as intervention HD and the other as the control.

Stratified random sampling will be used to select the students for the study from a sampling frame of the list of students in each classroom concerned.

We would use probability proportionate to size to choose the specific number of students to participate in the study per classroom (A, B, and C) for each class.

[figure not shown]

Figure 5: Selection of HAs and Schools for Implementation.

*GHS-Government High School; BGS-Bilingual Grammar School; GTHS Government Technical High School; GBHS government Bilingual High School

For each school distribution of the participants will be as follows:

A) For the Qualitative part:

The qualitative part will be sampled purposively.

Table 2: Number of Participants to be chosen per school for the FGDs

Health District	Schools	FGD Category of Participant	Number per school

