We will consider criteria for success as the proportion of persons who made an emergency call to an adult, teacher, the emergency number of the regional hospital, to a medical professional or to the closest Health Facility to the incident. The proportion of people who received help. The proportion of persons whose bleeds or LTBs were alleviated or attended to or who were referred for better management. Furthermore, the intention to treat/carryout the desired first aid act in the phase of an acute incident requiring FA. Lastly, we would like to evaluate the number of students who perform well during the scenarios to evaluate the need for knowledge revamping/refresher course on the aspects of FA taught. And all these, we shall compare the outcomes between the intervention and control groups.

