3.8 DATA COLLECTION TOOLS

A) Questionnaire

**Pre- and Post-Implementation of a Young First Aiders (YoFA) Training
Program Amongst Early Secondary School Children on Injury and Trauma
First Aid in Fako Division.**

Health District _____
Secondary School _____

Date: _____
Class: _____

A) QUESTIONNAIRE

Section 1

Please answer the questions below by **ENCIRCLING OR WRITING** the right answer you think is correct. If you do not know an answer, please select the answer you think is correct.

1. Gender	YES	or	NO
2. Age (in years):	_____		
3. Parents' Occupation:	Father _____ Mother _____		
4. Do you have access to a mobile phone all the time?	YES	or	NO
5. Have you heard the words First Aid?	YES	or	NO
6. Have you ever seen a traumatic injury? (A traumatic injury is an injury you sustain when something outside your body causes you to lose function or render you unable to use part or all of your body because of pain, bleeding or the because it is very serious)	YES	or	NO
7. A) Have you ever received any training in First Aid (formal or informal)?	YES	or	NO
B) If yes, briefly describe the training (where was it, what did you learn? How long ago was it?)			
Where? _____			
How long ago?			

 a) < 6months ago b) 6 to less than 12 months ago c) 1 to 3 years ago d) >3 years ago 			
What you learnt? _____			
<hr/>			
8. Have you ever seen someone bleeding and tried to stop that bleed yourself at home, school, marketplace, or anywhere else?	YES	or	NO
B) How many times has that happened? (Choose one)			

 a) Never b) Just once c) 2 to 5 times d) >5 times 			

C) What did you do to stop the bleeding? _____ **YES** or **NO**

D) Did it work? **YES** or **NO**

9. **A) Do you remember watching other people do this in the past?** **YES** or **NO**
B) Have you ever watched someone else offer such help in question 5? **YES** or **NO**

10. **If you find someone bleeding today,** **YES** or **NO**

A) Will you help them?

B) If 'no', why will you not help?

- I don't know what to do
- I am afraid I will make it worse
- I am afraid I will get into trouble
- I am afraid of blood
- Other reason _____

C) If 'yes', why will you help? _____

D) What steps will you take to help if 'yes'?

- Help by putting in toothpaste
- Help by applying pressure on the wound
- I will not help
- I will call an elderly person.

[figure not shown]
B) If you would not help, what makes you not want to help?

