3.11 DATA ANALYSIS PLAN

A difference-in-difference analysis would be done to assess the change in KAPs before and after the intervention in. The posttest would be done immediately after the 4 days of training for each pool and 3 months after the training to assess the need for refresher course planning.

The exposure variables include training on LTBs from injury first aid and the use of these services by the trained students (e.g., the number of persons assisted or referred during the follow-up period of the training).

We will analyze survey data using R Software with a combination of descriptive statistics and parametric and non-parametric tests to establish statistically significant differences between pre- and post-test results and between the intervention and control groups.

Table 7: Objectives and their Indicators

Objective	Activities/process	Data collection tools	Data Source	Indicators
1. To understand the perspectives of stakeholders on YoFA training program among SSC	- In-depth interviews	-In-depth interview guides	School teachers, administrators, parents, community leaders and students	
2. To assess school children's KAP (willingness and self-efficacy on trauma/injury FA via the built YoFA training to stop LTBs.	- survey	-Questionnaire	- students	- Obtain baseline KAP Scores
3. To evaluate the effectiveness and usability of the YoFA training program for SSC to respond to LTBs safely and promptly in their environs.	-Training following a specific STB and LFRs program -Training students on specific modules of LTB FA - Pre and post test -Simulation exercises	- Use adapted tools from the SBEAT - Questionnaires - Evaluation form with questions how? What was the situation?where, and how?	Stakeholders, teachers, parents, students	- Change in knowledge scores -At least 50% of stakeholders rate the program as good/ expectations met - 70% of students rate the program as good/expectations met - Number of children who made use of the FA skills taught
4. To determine the barriers associated with implementing the YoFA program among early SSC in the Fako Division.	- Interviews - Survey	-Interview guides - Questionnaires	- Stakeholders, - Teachers, students	- Perceived reasons and challenges that hinder FA training in schools.

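### Two pupil-level behaviour outcomes seen only in follow-up fall outside the difference-in-difference, and the stated comparison of two non-randomised schools makes no use of pretest items that could adjust for existing differences

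*Protocol*

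**What the plan says.** Section 3.6, Step 3, takes as criteria for success the proportion who made an emergency call, the proportions helped or attended to or referred, the intention to act, and performance in scenarios. It closes with "And all these, we shall compare the outcomes between the intervention and control groups". Section 3.7, outcome 5, counts participants who use the taught skills in the 3 months between training and final assessment.

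Section 3.11 applies difference-in-difference to change in KAP. Beyond that it names descriptive statistics and "parametric and non-parametric tests to establish statistically significant differences between pre- and post-test results and between the intervention and control groups". It names no covariate.

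Section 3.5 has one district chosen for intervention and the other for control, and does not say that chance decides. Table 5 puts one school in each arm, with 70 pupils each.

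The pretest in 3.8, taken by both arms, asks "Do you have access to a mobile phone all the time" (item 4), whether the pupil has had any first aid training (item 7A), and "Have you ever seen someone bleeding and tried to stop that bleed yourself at home, school, marketplace, or anywhere else" (item 8). Section 2.1 counts access "to a telephones availability of a teacher to guide them through" among the factors that enable the behaviour.

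**The concern.** Difference-in-difference removes a stable gap between schools only where the same quantity is measured before and after. No pretest item records past emergency calls, and use of the skills is counted only after training. For these two outcomes a gap that was already there looks the same as a training effect.

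The arms were not formed by chance, so balance cannot be assumed. The protocol itself gives reason to expect imbalance. Section 2.1 treats telephone access as enabling. Section 3.1 passes over Limbe because a lay first-responder programme there would confound the result, so other first aid activity is already seen as a confounder. Table 1 shows mean yearly trauma counts of 1280.5 in Tiko (control) and 487.75 in Buea (intervention).

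These outcomes bear on objective 3, that the programme is usable in school and community. A school difference could credit the programme wrongly, or hide a real effect.

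**Working it through.** **1. The plan's own figure.** Section 3.5 sizes the study for a "two-sample proportions test", "with a power of 80% and 5% error margin", assuming "a prevalence of the outcome in the controls of 0.5, and a prevalence in the intervention group of 0.75". The outcome is not named.

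n per group = [z(0.975)·√(2·p̄·(1−p̄)) + z(0.80)·√(p1(1−p1) + p2(1−p2))]² / (p2−p1)², with p̄ = 0.625.

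= [1.960·√0.46875 + 0.842·√0.4375]² / 0.0625 = (1.342 + 0.557)² / 0.0625 = 57.7, so 58 per group and 116 in total. Then 116 × 1.15 = 133.4, so 134. The stated figures reproduce and are not in dispute. The calculation is for a test without covariates.

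**2. Which criteria have a pretest counterpart.**
- Emergency call (3.6): none.
- Use of skills in 3 months (3.7, outcome 5): item 8 asks about any earlier attempt, ever. It can serve as a covariate, but it is not a matching 3-month period.
- Intention to act (3.6): item 10. Difference-in-difference can be used.
- Persons helped, or bleeds attended to or referred (3.6): none. These read as proportions of victims, not of pupils.

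**3. Size of the bias from one measured factor.** Inputs: 70 per arm (Table 5) and no training effect. The remaining inputs are assumptions, since the protocol gives none: phone access of 30% in the control school and 50%, 60% or 70% in the intervention school, and a call rate h with a phone and l without.

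Expected rate in a school with access a: p = a·h + (1−a)·l. Spurious difference = (a1 − a0)(h − l).

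Worked case, h = 50%, l = 20%, access 60% against 30%: p0 = 0.3·0.5 + 0.7·0.2 = 0.29; p1 = 0.6·0.5 + 0.4·0.2 = 0.38; difference 9 points. The pooled standard error is √(0.335·0.665·2/70) = 0.0798, so significance needs a difference of 1.96·0.0798 = 0.156. With the unpooled standard error of 0.0794, the chance of exceeding it is 1 − Φ((0.156 − 0.09)/0.0794), about 20%.

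Rejection rates of the unadjusted 5% test, from exact binomial sums:

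| Call rate with / without phone | 50% v 30% access | 60% v 30% | 70% v 30% |
|---|---|---|---|
| 50% / 20% | 12.0% | 20.5% | 31.8% |
| 20% / 8% | 6.9% | 9.4% | 12.7% |
| 30% / 20% | 6.0% | 7.1% | 8.6% |
| 25% / 20% | 5.4% | 5.6% | 6.1% |

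A steeper contrast gives more: 50% / 10% with access 60% against 30% gives about 35%. With equal access the rate stays near 5%.

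**4. Effect of adjusting.** In simulation with call rates of 50% / 20% (4,000 runs per setting), a Mantel-Haenszel test stratified on phone access rejected in 5.7%, 5.2% and 5.4% of trials for access of 50%, 60% and 70% against 30%. The crude test rejected in 12.3%, 21.3% and 32.0%.

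**5. What adjusting cannot do.** With call rates of 50% / 10%, access 60% against 30%, and a further unmeasured 10-point difference between the schools, the phone-adjusted analysis still rejected in about 23% of trials (2,000 runs).

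**The case against.** The strongest reply is that a covariate list is usually left to the statistical analysis plan, and that 3.11 never says its tests are unadjusted. That is fair as far as it goes. But 3.11 does state the methods: it applies difference-in-difference to KAP and names group tests otherwise. For outcomes without a pre-period in a non-randomised design, that is a weak choice as written, not just missing detail.

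Several limits stand:
- A reader might infer that no success criterion has a baseline. The protocol does not support this. Intention has item 10, section 3.3.2 says practices are assessed before and after training, and item 8 is a loose lifetime measure of earlier attempts.
- A call in 3.6 includes one to an adult or teacher, which may need no phone. The phone effect may therefore be small, and the lower rows of the table may be nearer the truth.
- A pupil-level model does not fit the victim-level proportions.
- Adjustment does not separate school from training. Opportunity to help may differ too, as Table 1 hints, though it gives no population denominators and 4.1 warns of incomplete reporting. That bias could run either way.

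**Conclusion.** The point holds for two outcomes: having made an emergency call, and having used first aid skills in the 3 months. Difference-in-difference does not cover them, and the stated comparison carries over school differences that the pretest already measures.

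For the call rates tabulated, the crude false-positive rate lies between about 5% and about 32%. This rests on 70 pupils per arm, no training effect, and access and call rates that are all assumed. It would be wrong to read the upper figures as the expected error. The protocol gives no rates, and with low or similar call rates most of the inflation disappears. It would also be wrong to read the adjusted result as free of confounding, because each arm is a single school. The change is worth making because it removes a recorded source of bias at little cost.

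**What to change.** In 3.11:
- Compare the two pupil-level outcomes by a regression on arm (risk difference or logistic), adjusted for pretest items 4, 7A and 8, with the crude figure alongside.
- Set an event threshold before the data are seen, below which only one covariate is used: item 4 for calls, item 8 for skill use.
- Word the skill-use outcome so that it applies to pupils who were not trained, since outcome 5 refers to skills the controls have not been taught.
- Report the result as an adjusted association, and state that school and training cannot be separated.
- Report the victim-level proportions descriptively by school.
- Keep difference-in-difference for the scored KAP outcomes and for intention (item 10).

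The cost is a few lines of text and a little more analysis in R. The three covariates are already in the pretest for both arms. The downside is some instability if events are few, which the single-covariate rule limits.

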3.7 STUDY VARIABLES AND TYPE

Variables

Outcome variables

1. Knowledge Change: to determine whether or not there was an overall change in knowledge before and after the training (dichotomous).
2. Test scores: to measure the educational efficacy of the first aid training before and after the intervention in comparison with the control group (continuous)
3. Self-efficacy ratings: Participants' self-perceived efficacy in performing first aid skills or their confidence levels in "Stopping the bleed and/or calling for help" (dichotomous)

4. Response time: The time taken by participants to respond to simulated first-aid scenarios or emergencies that require them to either stop an LTB or call for help or refer (continuous).
5. The number of participants who make use of the skills taught during the 3 months post-training but before the final assessment (Discrete).

Exposure Variables

The exposure variables include training on LTBs from injury first aid and the use of these services by the trained students (e.g., the number of persons assisted or referred during the follow up period of the training).

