will be a session for pretesting at the beginning of the intervention, at the immediate end, and 3 months after. **During the 3 months follow up period, we will visit the schools during their Wednesday club days every 2 weeks for 30mins to 1hour, to document their experiences and challenges in real time and their use of the skills.**

The qualitative part will take place before the quantitative pretesting of both groups begins.

Table 6: Plan of training and Evaluation of intervention groups

HA	School	N	Training Period in 2024	Date for Last Evaluation, 2024
Molyko (Intervention)	BGS Molyko	25	Nov 6 th , and 13 th	Feb 5 th
		25	Nov 20 th , and 27 th	Feb 19 th
		25	Dec 4 th and 11th	March 5 th
Mutengene (Control)	GHS Mutengene	70	November 6 th	Feb 26 th
	Total	145		

Step 3: Evaluation Phase

This comprises the evaluation of students' perceptions, barriers, and challenges in learning and applying the skills and lessons learned. It will equally involve evaluating parents' and stakeholders' perceptions about the program and including FA training in school curricula. It will involve the use of evaluation forms. This will take place about the same time as the post-three-month evaluation.

Knowledge will be assessed by evaluating whether the participants have ever heard of first aid or observed situations in which first aid was needed. They will be expected to have an increase in knowledge of first aid, especially regarding calling for help, stopping acute and life-threatening bleeds (LTB), and referrals after the training.

Before the training, we expect people not to have practiced first acts ever or to have

done it in a wrong way or to be scared to carry out specific first aid acts. After the training, we expect them to be more alert and identify situations needing first aid acts. Additionally, we expect their self-efficacy and confidence to perform first aid acts to increase and to effectively carry out first aid acts within their community or the school premises that will be documented using designed forms.

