3.9 DATA COLLECTION PROCEDURE

The qualitative data will be collected through FGD and in-depth interviews of the students and a simulation exercise. Interviews will be done using an interview guide until we reach a point of saturation. Each interview will last about 30 minutes.

Quantitative data will be collected on **three** first aid variables: first aid knowledge, practical skills, and helping behaviour (attitude) using pre and posttest questionnaires composed of multiple-choice questions. This will be done using an adapted evidence-based pretested tool called “Stop the Bleed” Education Assessment Tool (SBEAT)[20] in adaptation with the LFRs training tools.

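### Outcome 1 reduces knowledge to a yes/no change with no direction or minimum size, although the continuous score already collected is the better measure of gain

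*Protocol*

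**What the plan says.** Section 3.7 lists five outcome variables without labelling one as primary. The first, knowledge change, is "to determine whether or not there was an overall change in knowledge before and after the training (dichotomous". The second, test scores, is "to measure the educational efficacy of the first aid training before and after the intervention in comparison with the control group (continuous".

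The intended direction appears elsewhere. Section 1.1.2 says the pre-test and post-test are there to evaluate knowledge gained, Hypothesis 3 in section 1.6.2 speaks of improvement, and section 3.6 says of the pupils: "They will be expected to have an increase in knowledge of first aid". None of this is carried into outcome 1.

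The source of the yes/no variable is not settled either. Section 3.9 collects knowledge "using pre and posttest questionnaires composed of multiple-choice questions", whereas section 3.6 also says "Knowledge will be assessed by evaluating whether the participants have ever heard of first aid or observed situations in which first aid was needed". For the control group, section 3.6 states that there "will be a session for pretesting at the beginning of the intervention, at the immediate end, and 3 months after". There are thus two post-tests, and outcome 1 does not say which one counts.

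Section 1 of the questionnaire in section 3.8 opens by telling pupils: "If you do not know an answer, please select the answer you think is correct". Section 3.11 plans a difference-in-difference analysis, and its Table 7 names "Change in knowledge scores" as an indicator for objective 3.

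**The concern.** A yes/no change variable discards the two things the hypothesis is about: whether knowledge rose, and by how much. A pupil who loses two marks and a pupil who gains ten get the same code if the wording is followed literally.

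Supplying the obvious direction does not fully repair it. A multiple-choice score moves between two sittings without any learning, and the questionnaire encourages guessing. With no minimum size, a rise of one item makes a pupil a success. A sizeable share of controls would then be positive by chance, and the contrast between arms would be compressed. The first-listed outcome could look weak or null while outcome 2, from the same answer sheets, shows a clear gain.

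This is more than detail left for an analysis plan, because the Protocol itself fixes the variable as a dichotomous change.

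**Working it through.** **The plan's own figure.** Section 3.5 assumes 0.50 versus 0.75, two-sided alpha 0.05 and power 80%. With the pooled-variance formula, n = [1.960 × √(2 × 0.625 × 0.375) + 0.842 × √(0.5 × 0.5 + 0.75 × 0.25)]² / 0.25² = (1.342 + 0.557)² / 0.0625 ≈ 57.7, so 58 per group. This reproduces the stated 58. The calculation does not name its binary outcome. Outcomes 1 and 3 are the two labelled dichotomous in section 3.7.

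**Inputs for the noise check.** Items 13 to 37 of the questionnaire look scorable, which gives 25 items. Six of them (28, 31, 32, 34, 36, 37) are true/false. Everything else is assumed: one point per item, no true learning, each pupil answering a share f of items identically at both sittings, and the rest re-answered independently with probability p = 0.4 to 0.6 of being correct.

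**Formula.** With m unstable items, P(no change) = Σₖ [C(m,k) pᵏ (1−p)ᵐ⁻ᵏ]², and m is binomial with K items and probability 1 − f. Rises and falls are equally likely, so P(any gain) is half of P(any change).

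Hand check at p = 0.5, where P(no change) = C(2m,m)/4ᵐ with m held fixed:
- m = 25: 0.112, so 89% change and 44% rise.
- m = 12: 0.161, so 84% change and 42% rise.
- m = 5: 0.246, so 75% change and 38% rise.

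Letting m vary around its mean gives:

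| Items | Answers stable | Any change | Any gain |
|---|---|---|---|
| 25 | 0–50% | 84–89% | 42–44% |
| 25 | 80% | 73–74% | 36–37% |
| 25 | 90% | 59–60% | 29–30% |
| 15 | 0–50% | 79–86% | 39–43% |
| 15 | 80% | 63–64% | 32% |
| 15 | 90% | 46–47% | 23% |
| 10 | 0–50% | 74–82% | 37–41% |
| 10 | 80% | 54–55% | 27–28% |
| 10 | 90% | 35–36% | 18% |

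**What coarsening costs.** Simulation with 25 items, p = 0.5 and an assumed true gain of 4 items in trained pupils (trained versus untrained):

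| Definition | 50% stable | 80% stable |
|---|---|---|
| Any change | 96% v 84% (12 points) | 99% v 74% (25 points) |
| Any gain | 92% v 42% (50 points) | 99% v 37% (62 points) |
| Gain of 3 or more items | 73% v 16% (57 points) | 84% v 5% (79 points) |

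**Power near the ceiling.** At 70 per group (Table 5), the normal approximation for two proportions gives 38% for 0.80 v 0.90, 50% for 0.85 v 0.95, 77% for 0.80 v 0.95 and 92% for 0.75 v 0.95.

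**The case against.** The best defence is that section 3.7 is a short list of names and types, that a cut-off can be set in an analysis plan, and that the direction is plain from the rest of the Protocol. The word overall may also mean a single group-level verdict and not a code for each pupil. The main remedy is already present: outcome 2 is continuous and compared with control, the analysis is difference-in-difference, and Table 7 points to scores. Nothing makes outcome 1 primary.

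Much of this stands. It limits the consequences, and it rules out four stronger readings that a reader might infer:

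- *Pupils who get worse are meant to count as successes.* They are not. The aims say otherwise, and the success criteria in section 3.6 do not mention outcome 1.
- *Most untrained pupils would certainly be positive.* No retest reliability or scoring rule is given. Some items are rankings or take several answers, so 25 single points is a guess. For 10–15 items with 90% of answers stable, fewer than half change. If knowledge means having heard of or observed first aid, the noise model does not apply.
- *The variable cannot separate the arms.* It can: 0.75 v 0.95 has about 92% power at 70 per group. The loss is of efficiency.
- *The sample size is wrong because of outcome 1.* Section 3.5 does not tie its calculation to outcome 1, and its arithmetic reproduces.

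The defence does not remove the core. Adding the intended direction still leaves any gain with no minimum size, and a group-level verdict would still lack a decision rule.

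**Conclusion.** The point holds in a limited form. Outcome 1 is fixed as a yes/no change without direction or minimum size, while the Protocol's aims concern gain. On the charitable reading of any gain, about 37–44% of untrained pupils could be classed as improved with 25 items and 0–80% of answers stable, and fewer on a shorter or more stable test. On the literal reading, about 73–89% would be positive under those same assumptions, about 60% with 90% stable, and 35–47% for 10–15 items with 90% stable. Half of those changes would be falls.

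All of these percentages rest on assumed test length, scoring and answer stability. The lack of direction and size does not depend on them. The variable is inefficient and open to misreading. Outcome 2 and the difference-in-difference analysis contain the harm, so this is a worthwhile correction to one outcome and not a threat to the trial's main comparison.

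**What to change.** In section 3.7, make the continuous knowledge score (outcome 2), compared between arms by the planned difference-in-difference, the measure of knowledge gain. Drop any change as an outcome.

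If a yes/no version is wanted for policy readers, define it as an improvement of at least a stated number of items, or as reaching a fixed mastery mark. A mastery mark measures the level reached and not the change, so the text should say which is meant. Name the post-test (immediate or 3 months), use the same rule in both arms, and set it before scores are analysed.

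The cost is a line or two in section 3.7 and no new data. The one small burden is that a cut-off must be chosen and justified if the binary version stays.
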